4.2. Safety Measures

Safety will be measured by assessing all adverse events experienced by patients related or probably related to the study device. Adverse events will be documented at the intra-operative and all postoperative evaluation intervals to determine the safety profile of the device. The incidence of surgery- and device-related events such as device revision, component failure, malfunction, migration, subluxation, dislocation, loosening, nerve damage, deep infection, deep vein thrombosis, pulmonary embolism, or bone breakage/fracture will be collected. Some events may not be evident until after a long-term follow-up such as evidence of severe osteolysis, excessive articular surface wear, or significant debris production. All adverse events in study patients between enrollment and ten years shall be reported at the time of occurrence. Efficacy and safety measurement will be performed as summarized in the study schematic presented in Table 1.

5. Study Population

This clinical study can fulfill its objectives only if appropriate subjects are enrolled. All relevant medical and non-medical

conditions should be taken into consideration when deciding whether a particular patient is suitable.

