8. SAFETY REPORTING

An adverse event assessment will be conducted at each follow-up interval. Data from each visit will be recorded on the study CRFs. All adverse events, regardless of their relationship to the study device, occurring from the time of study device implantation through to study completion should be recorded on the appropriate CRFs and reported as below.

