concern to the subject and/or poses substantial risk to the subject's health or well-being. The event is likely to require medical intervention and/or close follow-up and may be incapacitating or life threatening. Hospitalization and treatment may be required.

The Investigator is responsible for assessing the relationship of the AE to the study device and study procedure based on the following definitions:

- Unrelated: the event is clearly not related to the study device or study procedure
- Possible: the event may or may not be related to the study device or study procedure. A relationship cannot be ruled out.
- Probable: the event is likely related to the study device or study procedure. A relationship cannot be ruled out.
- Definite: the event is clearly related to the study device or study procedure.

D. Reoperation and Revisions

A reoperation is any surgical procedure of the study hip. A revision is a surgical procedure of the study hip where one or more of the study components are removed and replaced with new implants.

All reoperations and study component revisions should be documented on the Adverse Event CRF.

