4 STUDY OBJECTIVES

The objective of this study is to determine the long-term safety and effectiveness of the R3 Acetabular System by analysing the clinical, radiographic responses and the adverse event rates for

CONFIDENTIAL AND PROPRIETARY

This document contains information that is confidential and proprietary to Smith & Nephew PLC and Smith & Nephew, Inc. and is intended for use only by Smith+Nephew and its manufacturer. It shall not be reproduced or copied in whole or in part, nor shall the contents be disclosed by any means without prior written permission from Smith+Nephew, nor shall anyone make any use of it that is contrary to the expressed or implied wishes of Smith+Nephew.

Statistical Analysis Plan

A prospective, multicenter, non-randomized, clinical outcomes study of the R3[◊] Acetabular System in patients with degenerative hip disease

Number:
R3H01/02/01/2017
ST: 1103
Version: 3.0
Page: 7 of 18

patients undergoing primary total hip arthroplasty using the R3 Hip System (R3 Acetabular System). The study hypothesis is as follows: implant survivorship (Kaplan-Meier) (revision for any reason) of the R3 cup is at least 97% at 3 years, 95% at 5 years, 93% at 7 years, and 90% at 10 years follow-up.

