5.3 Safety Endpoints

The safety endpoints are as follows:

- Incidence of Adverse Events by International Organization for Standardization (ISO) classifications
- Incidence of AEs by severity,
- Incidence of AEs by relationship to study device,
- Incidence of serious adverse events (SAEs),
- Incidence of Serious Adverse Device Effects (SADEs),
- Incidence of Unanticipated Serious Adverse Device Effects (USADEs),
- Incidence of Anticipated Serious Adverse Device Effects (ASADEs),
- Incidence of procedure-and or device related events,

CONFIDENTIAL AND PROPRIETARY

This document contains information that is confidential and proprietary to Smith & Nephew PLC and Smith & Nephew, Inc. and is intended for use only by Smith+Nephew and its manufacturer. It shall not be reproduced or copied in whole or in part, nor shall the contents be disclosed by any means without prior written permission from Smith+Nephew, nor shall anyone make any use of it that is contrary to the expressed or implied wishes of Smith+Nephew.

Statistical Analysis Plan

A prospective, multicenter, non-randomized, clinical outcomes study of the R3[◊] Acetabular System in patients with degenerative hip disease

Number:
R3H01/02/01/2017
ST: 1103
Version: 3.0
Page: 8 of 18

- Listing of revisions and components revised.

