7.11 Analysis of Safety Endpoints

An overall summary AE table that would summarize as number (n) and percentages (%), the overall incidence according to subjects (and hips) with at least one AE; subjects (and hips) with at least one AE by worst severity (mild, moderate, or severe), by worst outcome (resolved, ongoing/unresolved, death or removal/revision of components), worse relatedness to device, SAEs, ADEs, SADEs, ASADEs and, USADEs. Classification of AEs would also be summarized using ISO classifications. A data listing with all AEs (and their classifications) reported on-study will be presented. Finally, the incidence of device-and/or procedure related AE by their type will be presented too.

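### SAP 7.11 plans incidence by event type only for adverse events rated device- or procedure-related; an all-event column should stand beside it

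*SAP*

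**What the plan says.** The protocol collects broadly. Section 8 requires that "All adverse events, regardless of their relationship to the study device" be recorded, from implantation to the end of the study. Section 8.1 has the investigator rate each event against device and procedure as Unrelated, Possible, Probable or Definite. The lowest level reads "Unrelated: the event is clearly not related to the study device or study procedure".

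SAP 7.11 then plans four outputs:

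1. an overall table of subjects and hips with any event, split by worst severity, worst outcome (including removal or revision), relatedness to the device, and the seriousness and device-effect classes;
2. an ISO summary: "Classification of AEs would also be summarized using ISO classifications";
3. a listing of all events;
4. a by-type table: "the incidence of device-and/or procedure related AE by their type will be presented too".

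The endpoint list in SAP 5.3 matches. It contains "Incidence of Adverse Events by International Organization for Standardization (ISO) classifications" and "Incidence of procedure-and or device related events", but no incidence by event type for all events.

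The primary hypothesis in SAP 4 concerns "implant survivorship (Kaplan-Meier) (revision for any reason) of the R3 cup", which takes no account of relatedness.

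**The concern.** Output 4 is the only table that the SAP says will give a rate for a particular kind of event, and an event enters it only through a causality judgement. The site investigator makes that judgement in an observational cohort with no randomised comparator. The supplied text describes no independent review of it, whereas Protocol 7.4 does provide independent review of the radiographic observations.

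With no control group, the absolute rates of dislocation, deep infection or fracture are themselves the safety result, and no second arm shares any attribution error. A late deep infection, or a fracture after a fall, could be rated Unrelated, lead to revision and count as a failure in SAP 7.9, yet not appear in the by-type table. No planned summary sets the revisions beside the underlying event type and rating. The all-event listing contains the case, but a listing is not an incidence.

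**Working it through.** The plan gives no figure to reproduce here. The check is mainly a comparison of texts.

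**Which planned outputs give event type without a relatedness filter?**

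| Output | Filtered by relatedness? | Gives incidence by event type? |
|---|---|---|
| Overall table (SAP 7.11) | No | No: severity, outcome, device relatedness and seriousness classes only |
| ISO summary (SAP 5.3, 7.11) | No | Cannot be determined: the classification is not defined |
| All-event listing (SAP 7.11) | No | No: single events, not a rate |
| By-type table (SAP 7.11) | Yes | Yes |
| Radiographic findings (SAP 7.10) | No | Partly: radiographic signs by visit |
| Revisions (SAP 5.3 listing, 7.9) | No | No: a survival estimate, and a listing with the components revised |

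Only the by-type table is stated to be by type, and it is filtered.

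**Which ratings pass the filter?** The SAP does not say, and the protocol's wording varies:

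- Protocol 4.2 measures safety through events related or probably related to the device, which on its face leaves out Possible.
- Protocol 8.2, on prompt reporting to the sponsor, covers possible, probable and definite.
- Protocol 9 refers to device-related events without naming levels.

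If Possible counts as related, an event drops out only when it is clearly unrelated to both device and procedure. If Possible does not count, more events drop out.

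**How large could the effect be?** Let x be the number of subjects with a given event, u the share left out by the filter, and N the denominator. The incidence shown is x(1 − u)/N. N = 512 is the number of subjects enrolled (SAP 6.1). It is used for illustration only: it is neither a count of hips nor the size of the safety population, and the documents give neither. Both x and u are assumptions.

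| x | u = 0 | u = 10% | u = 25% | u = 40% |
|---|---|---|---|---|
| 20 | 20/512 = 3.91% | 18/512 = 3.52% | 15/512 = 2.93% | 12/512 = 2.34% |

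For a rarer event, x = 10 gives 10/512 = 1.95% (exact 95% CI 0.94 to 3.56). With u = 10% the table shows 9/512 = 1.76%. With u = 50% it shows 5/512 = 0.98% (0.32 to 2.26). With u = 0 nothing changes. The documents give no information on u.

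**The case against.** The strongest reply is that the by-type table is what the protocol asked for. Protocol 4.2 lists "device revision, component failure, malfunction, migration, subluxation, dislocation, loosening" and further events, but introduces them as surgery- and device-related events. Protocol 9 plans a summary of device-related events, and SAP 5.3 names related events as an endpoint. This stands: the SAP does not depart from the protocol, and an all-event table is an addition.

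The reply also says that the exclusion is narrow. A rating of Unrelated requires a clear absence of relation to both device and procedure, and a dislocation or loosening will seldom meet that. This stands if Possible counts as related, which the SAP does not settle.

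A reader might infer three stronger things that the documents do not support.

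- *That such events vanish from every event-specific rate.* The ISO summary is unfiltered and, being undefined, might carry event type. Radiographic findings are tabulated whatever the event rating. The table shells, named in SAP 2 as a related document, were not available and might contain an all-event table.
- *That the planned rates can only be too low.* The related count cannot exceed the all-event count, but the two are different quantities. The all-event rate includes events that truly have nothing to do with the implant. A related rate that admits Possible may include some of these too.
- *That by-type events and revisions cannot be reconciled.* Protocol 8.1 puts every revision on the adverse event form, and the SAP lists both revisions and all events. Each case can be traced by hand; what is missing is a planned summary that does so.

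**Conclusion.** The point holds as a reporting weakness. The only adverse-event table stated to be by type depends on the investigator's attribution, with an unstated cut-off, and no all-event incidence by type is stated although the data are collected. The gap matters most for deep infection, fracture and dislocation. Radiographic tables partly cover loosening and migration, and events that end in revision are captured in SAP 7.9 and the revision listing, though without a rate by underlying type.

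The size is unknown. The illustrated falls, from 3.91% to between 3.52% and 2.34%, rest wholly on assumed event counts and assumed shares rated unrelated, over enrolled subjects. The real effect could be near zero. No primary result and no figure in the documents changes. The case for acting is that the change costs almost nothing and removes the dependence on attribution.

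**What to change.** In SAP 7.11, present incidence by type for all adverse events in the safety population, for subjects and for hips, with the device- and/or procedure-related subset as a second column. State which of the four ratings count as related. Define the ISO classification, so that a reader can tell whether it carries event type. Optionally, add the underlying event type and relatedness rating to the listing of revisions, so that it can be read against SAP 7.9.

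Cost: a sentence or two in the SAP and one extra column. SAP 6.3 states that the last subject's last visit has taken place, and all events are already recorded, so no new data are needed. The downside is that the all-event rates will include some events truly unrelated to the implant; the second column separates these.

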7.12 Additional Analysis

Type of R3 bearing would be classified into meaningful subgroups by the Clinical Strategy team using Head/Inlay/Inlay Material available in the database. Implant survivorship would subsequently be summarized exploratorily for each of the classified subgroup of the R3 bearing (head/inlay: i.e. Biolox delta ceramic-on-ceramic, Biolox forte ceramic-on-ceramic, Oxidized zirconium-on-

CONFIDENTIAL AND PROPRIETARY

This document contains information that is confidential and proprietary to Smith & Nephew PLC and Smith & Nephew, Inc. and is intended for use only by Smith+Nephew and its manufacturer. It shall not be reproduced or copied in whole or in part, nor shall the contents be disclosed by any means without prior written permission from Smith+Nephew, nor shall anyone make any use of it that is contrary to the expressed or implied wishes of Smith+Nephew.

Statistical Analysis Plan

A prospective, multicenter, non-randomized, clinical outcomes study of the R3[◊] Acetabular System in patients with degenerative hip disease

Number:
R3H01/02/01/2017
ST: 1103
Version: 3.0
Page: 17 of 18

crosslinked polyethylene, Ceramic-on-crosslinked polyethylene, Metal-on-crosslinked polyethylene and Metal-on-metal) using Kaplan-Meier survival methods as described in Section 7.9.

The analysis population for these analyses would be the FAS population.

7.13 Other Data Summaries

Not applicable.

7.14 Changes in Analysis Methods Specified in the Protocol

The protocol-specified hypothesis is now more carefully elucidated in this SAP.

The primary analysis population of the primary endpoint is now specified to the based on the FAS population.

After consultation between key study stakeholders, it was determined that the additional COVID-related analyses previously included in SAP final version 1.0 would be of negligible-to-no impact on the results and therefore this is removed from this amendment.

Additional exploratory analysis of the primary endpoint by head/inlay material was added on request by Clinical Strategy.

CONFIDENTIAL AND PROPRIETARY

This document contains information that is confidential and proprietary to Smith & Nephew PLC and Smith & Nephew, Inc. and is intended for use only by Smith+Nephew and its manufacturer. It shall not be reproduced or copied in whole or in part, nor shall the contents be disclosed by any means without prior written permission from Smith+Nephew, nor shall anyone make any use of it that is contrary to the expressed or implied wishes of Smith+Nephew.

Statistical Analysis Plan

A prospective, multicenter, non-randomized, clinical outcomes study of the R3[◊] Acetabular System in patients with degenerative hip disease

Number:
R3H01/02/01/2017
ST: 1103
Version: 3.0
Page: 18 of 18

